## Section 8 – Data and Safety Monitoring –Greater than Minimal Risk Study

- For all research that is greater than minimal risk a Data and Safety Monitoring Plan must be developed.
- This is a plan to assure the research includes a system of appropriate oversight and monitoring of the conduct of the study to ensure the safety of subjects and the validity and integrity of the data.

| *CHECK BOX IF THIS IS A MINIMAL RISK 5 63. Safety monitoring for this greater than minim  |   |
|---|---|
| ☐ Data Safety Monitoring Board:   |   |
| ☐ Data Monitoring Committee   |   |
| Other   |   |
| 
 
Attach the plan or provide details included sponsor, how often it meets, whether wr
 
                                   | ding whether committee is independent from the study
itten reports are available, etc  |
| independent observer (e.g., [name]
uninvolved with the study (e.g., [name]
meet annually to review study procedures an | [name], Chief of Neurology). The Committee will doutcomes, and analyze adverse events to identify nticipated issues that may affect the risk profile for                  |
| 64. Describe the plan for on-site data monitoring (CRO), or other independent body:   | g by the sponsor, contract research organization  |
| during the course of the study and will take  | nal audits and monitoring are anticipated once
e place in accordance with all applicable policies
ecessary, external entities will be contracted to
project funds. |
| • *Research Office must be notified of all  | on-site monitoring visits.  |
| 65. Conditions that may result in removal of sub  | jects from the research (check all that apply):   |
| Medical condition unchanged   | Medical condition worsened  |
| Serious adverse event   | ☐ Intolerable complications   |
| □ Pregnancy   | ☐ Investigator's clinical judgment  |
| Subject withdrawal  | Subject uncooperative or noncompliant   |
| Study closure by sponsor or FDA   | Refusal to suspend breast-feeding   |
| Other-describe:   | ☐ Not Applicable  |
| 66. If a subject withdraws or is removed from the withdrawal and the procedures in place to m   | ne study, describe the potential risks of early inimize these risks:  |

If participants withdraw from the study prior to implantation, there should be no increased risk

related to the study. If the participant is implanted and chooses to withdraw, we retrieve the external equipment which prevents further use of the Implant. The implant can remain in place or can be removed, depending on the desire of the participant. The implant can remain in place without causing health problems for the participant.

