#### Infection:

There is a risk that the implanted stimulator could be infected. To reduce the likelihood of infection, special steps (including extensive cleaning of the skin prior to surgery, taking antibiotic medication before and after the operation, and performing the procedure in an operating room) will be taken. As with any other implanted material, there is the risk that the blood can carry bacteria or other infectious agents to the location of the stimulator(s) or electrodes where they can collect and multiply long after the time of surgery. An infection of this type is a known complication for artificial joints and other implants. An aggressive antibiotic treatment would be prescribed to treat the infection and if unsuccessful the device

would be removed in a second surgical procedure. This has occurred once with a lower extremity implant and the subject fully recovered after the device was removed.

To reduce the risk of such systemic infections, it is important for participants to seek medical treatment quickly for any cold, flu, or respiratory or viral infection. Open wounds, burns or dental cavities should also be treated rapidly since they can be sources of infection. Subjects should monitor themselves for urinary tract infections or pressure injuries, and take the other reasonable precautions required for someone with paralysis to remain in good health.

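### Item 66 assures the IRB without qualification that a withdrawn subject's implant can stay in harmlessly, which item 38's own list of hardware risks contradicts

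*Combined protocol and SAP*

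**What the plan says.** Item 66 in Section 8 puts a two-part question: what are the potential risks of leaving early, and what is done to reduce them. The question covers both routes out ("If a subject withdraws or is removed from" the study).

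For subjects not yet implanted, the answer is that no added risk is expected. For implanted subjects it opens with "If the participant is implanted and chooses to withdraw" and makes three statements:

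- Equipment: "we retrieve the external equipment which prevents further use of the Implant".
- Choice: "The implant can remain in place or can be removed, depending on the desire of the participant".
- Assurance: "The implant can remain in place without causing health problems for the participant".

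Nothing else is said there about implanted subjects who leave. Item 66 names no risk and no precaution, gives no contact arrangement, and does not refer back to item 38.

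**The concern.** Item 66 is where the IRB is told what happens to someone who leaves the study with a stimulator, leads and nerve cuffs in the body. The question asks for risks, and the answer says there are none. The risk section of the same protocol describes several hazards that belong to the hardware rather than to its use, so the two parts cannot both be taken literally.

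The stake is subject safety and accurate disclosure to the IRB. If the sentence stands, the IRB has no stated reason to ask how a late infection or skin breakdown would be picked up in someone no longer in the study, or whether that person leaves with the imaging and diathermy warnings in hand.

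**Working it through.** No arithmetic underlies the sentence and the plan gives no figure to reproduce. The check is to set item 66 beside item 38 and ask of each hazard whether retrieving the external equipment ends it.

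| Subsection of item 38 | What it describes | Ended by retrieving the controller? |
|---|---|---|
| Infection | Organisms carried in the blood settle on stimulator or electrodes, "where they can collect and multiply long after the time of surgery"; one past lower extremity device was removed for infection, timing not given | No |
| Tissue erosion | Pressure over implant or leads can break down skin and expose components | No |
| Nerve or vessel injury | A cuff can compress the nerve, with permanent damage possible; onset is described mainly as days or weeks after surgery, though scar build-up is a listed cause | No, but mostly an early risk |
| Pregnancy and birth defects | Leads do not stretch and may press on skin or organs | No; only the stimulation part of this risk ends |
| MRI; Diathermy | No MRI anywhere; no diathermy near the device; contact investigators before nearby surgery | No; these apply while hardware is present |

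Electrode movement and breakage are left out of the table because their stated effects mostly concern stimulation. Scarring is left out because the protocol reports that it has not been seen.

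**What supports good tolerance.** Item 38 says the implanted parts are passive and hold no batteries (Burns and electrical hazards), and that material left after electrode removal is usually harmless (Electrode movement and/or breakage). That supports a statement that retained hardware is usually tolerated. It does not support one with no exceptions.

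**The other branch of the choice.** Item 66 offers removal without describing it. Under Infection, item 38 says an infected device that antibiotics do not clear "would be removed in a second surgical procedure". Under Electrode movement and/or breakage, it says a variable amount of material is left behind on removal. Both options therefore carry a cost that item 66 does not mention.

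**What changes at exit.** Enrolled subjects carry the same hardware hazards. Withdrawal may change who is watching. Section 3, item 13 (Discharge and Follow-up) provides regular telephone or electronic monitoring of medical conditions after discharge. Item 66 does not say whether this continues for someone who has left.

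**Who is covered.** The question includes subjects who are removed, while the answer for implanted subjects addresses only those who choose to go.

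**Size.** Section 4, item 20 gives 15 new recipients and 10 previous recipients: 15 + 10 = 25 implanted people at most. The hardware of the previous 10 may also be followed under other protocols. The number who would leave is not given, so no expected count can be worked out.

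**The case against.** The strongest reply is that item 66 asks about the risk added by leaving, and an unpowered device left in place adds none beyond what every recipient already carries. The IRB reader also has the full hardware list in item 38, and nothing there says that the precautions lapse at withdrawal. On this view the gap is editorial. Part of this stands: the precautions exist in the protocol, and the fault is that item 66 does not carry them over. But the preceding sentence of item 66 already gives permission to keep the device. The last one adds a safety assurance, and as worded it reaches well beyond added risk.

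A reader might infer more than the documents show, in three ways:

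- **That subjects choose to keep the implant on the strength of this sentence.** The Research Plan is written for the IRB. Subjects decide from consent forms (Section 6, item 45), discussion with staff, and a user manual (Section 10, item 76). The forms and manual were not available, and no claim is made about them.
- **That a withdrawn subject loses a countable share of device surveillance, namely the visits at about 6 to 12 and 18 to 24 months.** Item 13 says only that subjects may be asked to repeat tests then, and those are mainly performance tests. Its checks of the implanted components rely on stimulation, which ends once the controller is returned. The relevant contact is the telephone monitoring, and its fate is simply unstated.
- **That a removed subject would be treated differently from one who withdraws.** Nothing suggests this; the text just does not address it.

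The MRI and diathermy limits restrict other procedures and so contradict the assurance less directly than infection or erosion. They still belong in an answer about leaving with hardware in place.

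**Conclusion.** The point holds as a conflict within the protocol and an incomplete answer in item 66. The unqualified assurance disagrees with item 38 on late infection and skin erosion most clearly, and on nerve compression and pregnancy to a lesser degree. Item 66 also leaves out the lasting restrictions, the surgical nature and limits of removal, and whether telephone monitoring goes on.

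It should be fixed because it bears on safety and costs little. It applies to at most 25 people, and how many would be affected is unknown because the protocol gives neither a withdrawal rate nor a late-event rate. No statistical result is touched. The conclusion rests on the text of items 13, 38 and 66 alone; the consent forms or the manual may already deal with some of this.

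**What to change.** Replace the last sentence of item 66 with wording such as: *Retained hardware is usually tolerated, but the item 38 risks of late infection, skin erosion, nerve compression and lead pressure in pregnancy remain, as do the MRI and diathermy restrictions; removal is a further surgical procedure and may leave some electrode material behind.* Then:

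- State that this applies to subjects who withdraw and to those who are removed.
- At exit, give each subject who keeps hardware the precautions from the Tissue erosion, MRI and Diathermy parts of item 38, with a contact route that does not end with participation. A route tied to study closure would not cover the infection risk that item 38 places long after surgery.
- For subjects who agree, continue the telephone contact of item 13 for device-related events, and report these to the safety committee in item 63, which is to "meet annually to review study procedures" and outcomes.

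The cost is one IRB amendment, possibly with matching text in the implant consent form, and a few calls per consenting subject. The protocol gives no call interval. If calls were made every 3 to 6 months, which is an assumption, that is 12/6 = 2 to 12/3 = 4 per subject per year. Some subjects will decline, and for them the exit information and contact route are the safeguard.

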## Section 9 - FDA-Regulated Drugs/Biologics

NOTE: If this research involves the use of any drugs or biologics, the study is subject to the Food and Drug Administration (FDA) regulations.

- Documentation of FDA approval for the experimental use of these agents must be provided for review (industry sponsored protocol listing the IND number, letter from the FDA, letter from industry sponsor, or other document and/or communication verifying the IND for this study).
- All drug/biologic products must be dispensed and tracked through the LSCDVAMC Research Pharmacy.
- An M.D. must be part of the Research Team for all studies that involve the use of a device or drugs.
- The LSCDVAMC Pharmacy and Therapeutics (P&T) Committee must approve: (1) Studies of investigational drugs (2) research involving an FDA-approved drug used in a non-approved manner, and (3) an FDA-approved drug, used as approved, when its use is part of a research protocol.
- VA Form 10-9012 Investigational Drug Information Record —must be completed for each drug being evaluated in a research study, regardless of IND status. In addition, the VA Form 10-9012 provides a listing of all authorized prescribers for the study drug(s).

| 67. | Type of Product- check all that apply:  |
|-----|---|
|     | Not Applicable -No FDA-regulated drugs/biologics involved − Proceed to Section 10   |
|     | ☐ Drug  |
|     | ☐ Biologic or Other:  |
| 68. | Type of Trial (check as applicable):  |
|     | ☐ Phase I ☐ Phase III ☐ Phase IV ☐ NA   |
|     | Phase I Trials: Initial studies to determine the metabolism and pharmacologic actions of drugs in humans, the side effects associated with increasing doses, and to gain early evidence of effectiveness; may include healthy subjects and/or patients.  Phase II Trials: Controlled clinical studies conducted to evaluate the effectiveness of the drug for a particular indication or indications in patients with the disease or condition under study and to determine the common short-term side effects and risks.  Phase III Trials: Expanded controlled and uncontrolled trials after preliminary evidence suggesting effectiveness of the drug has been obtained, and are intended to gather additional information to evaluate the |
|     | overall benefit-risk relationship of the drug and provide adequate basis for physician labeling.  Phase IV Trials: Post-marketing studies to delineate additional information including the drug's risks,   |

## 69. FDA Status of Drugs/Biologics -

benefits, and optimal use.

# \* For drugs, an IND may not be necessary if ALL seven of the following conditions are met:

- 1. The drug being used in the research is lawfully marketed in the United States;
- 2. The research is not intended to be reported to FDA in support of a new indication for use or to support any other significant change in the labeling for the drug;
- 3. The research is not intended to support a significant change in the advertising for the product;
- 4. The research does not involve a route of administration or dosage level, use in a subject population, or other factor that significantly increases the risks (or decreases the acceptability of the risks) associated with the use of the drug product;

- 5. The research is conducted in compliance with the requirements for IRB review and informed consent (21 CFR parts 56 and 50, respectively);
- 6. The research is conducted in compliance with the requirements concerning the promotion and sale of drugs (21 CFR 312.7);
- 7. The research does not intend to invoke 21 CFR 50.24 (Exception from informed consent requirements for emergency research).

#### Provide the following information for each drug/biologic used in this study:

| Trade and
Generic Name | Manufacturer | FDA
Approved | Product use consistent with product labeling | IND
Required* | IND Number | IND Sponsor or
Holder** |
|---------------------------|--------------|-----------------|--|------------------|------------|----------------------------|
|                           |              |                 |  |                  |            |                            |

| 70. | **When | the PI | holds th | ie IND, | complete the | following: |
|-----|--------|--------|----------|---------|--------------|------------|
|-----|--------|--------|----------|---------|--------------|------------|

i. The PI has reviewed the Guidance on Requirements of the Sponsor and the Investigator as Sponsor

☐ Yes

ii. As the PI, you will comply with the regulatory responsibilities of a sponsor

Yes

71. Drug Information for each drug listed in the protocol -check as applicable

☐ Approved Drugs

☐ Not Approved

- Attach VA Form 10-9012 Investigational Drug Information Record for each drug used in the protocol
- Attach Package Insert or PDR monograph copy ready, 8.5 x 11 for each drug listed in the protocol
- Attach Investigator's Brochure
- 72. Provide a detailed description of how FDA-regulated drugs/biologics will be stored, secured, dispensed, administered, tracked, and returned.

## Section 10 - FDA-Regulated Devices

This section should be completed for a medical device that is the subject of a clinical study designed to evaluate the effectiveness and/or safety of the device.

An investigational device may be an FDA approved device that is being studied for an unapproved use or
efficacy. This also includes an approved device that is being studied for an unapproved or approved use in
a controlled, randomized, or blinded clinical trial.

 Documentation of FDA approval for the experimental use of the device must be provided for review (industry sponsored protocol listing the IDE number, letter from the FDA, letter from industry sponsor, or other document and/or communication verifying the IDE for this study).

#### **Device Risk Determination:**

**Significant Risk (SR) Device** is an investigational device that: (1) is intended as an implant and presents a potential for serious risk to the health, safety, or welfare of a subject, or (2) is purported or represented to be for a use in supporting or sustaining human life and presents a potential for serious risk to the health, safety, or welfare of a subject; or (3) is for a use of substantial importance in diagnosing, curing, mitigating, or treating disease, or otherwise preventing impairment of human health and presents a potential for serious risk to the health, safety, or welfare of a subject; or (4) otherwise presents a potential for serious risk to the health, safety, or welfare of a subject.

Non significant Risk (NSR) Device is a device other than a significant risk device.

The IRB is required to document the basis for risk determination based on the proposed use of a device in the research by considering the nature of the harm that may result from the use of the device. FDA has the ultimate decision in determining SR and NSR.

An M.D. must be part of the Research Team for all studies that involve the use of a device.

The Environment of Care Committee (EOC) must approve all research that involves electrically line-operated devices, which have leads or electrodes and will come in contact with human subjects.

| 73  | Type | of Pro | duct-o  | heck | all    | that  | apply: |
|-----|------|--------|---------|------|--------|-------|--------|
| 10. | Lype | OIXIO  | tauct t |      | 54 A A | CHARL | uppyj. |

| Not Applicable -No FDA-regulated devices involved – Proceed to Section 11)              |
|---|
| An FDA regulated device will be used BUT not with intent of studying safety or efficacy |
| (Proceed to Section 11)   |
| ⊠ Device  |

#### 74. List the device-include name and manufacturer:

| Implantable Stimulator Telemeter (IST 16)   | TDL (Technical development laboratory of the Cleveland FNS Center)  |
|---|---|
| External Controller  UECU/UECU Lite  Wireless Finger Switch/Sensor  Wireless accelerometer/gyroscope  Communicating Coil  Charger  Stimulation Software | Ardiem Medical, Inc. [name] [contact]  TDL- Technical Development Laboratory Case Western Reserve University [name] [contact] |

#### 75. FDA Regulatory Status of the Device:

#### ☐ FDA Approved Device

A device approved by the FDA for distribution, marketing, sale to, and use by, the public for the study's indication.

|             | New Indication of an FDA Approved Device  |
|-------------|---|
|             | • A device NOT approved by the FDA for distribution, marketing, sale to, and use by the public for the indication used in the study.  |
| $\boxtimes$ | Investigational - Investigational Device Exemption (IDE)  |
|             | • An FDA designation that permits a manufacturer to lawfully ship an unapproved device for use in a research study.   |
| Provide t   | the following:  |
|             | a. IDE Number: IDE# G040214 & IDE#G900108  |
|             | b. IDE Sponsor or Holder: VA Research Office  |
| If the P    | I holds the IDE, complete the following:  |
|             | i. The PI reviewed the Guidance on Requirements of the Sponsor and the Investigator as Sponsor  |
|             | Yes   |
|             | ii. As the PI, you will comply with the regulatory responsibilities of a sponsor  |
|             | ☐ Yes   |
|             | c. FDA or Sponsor Device Risk Determination   |
|             | Non-Significant Risk  |
|             |   |
|             | d. Attach documentation of FDA approval for the experimental use of the device (industry sponsored protocol listing the IDE number, letter from the FDA, letter from industry sponsor, or other document and/or communication verifying the IDE for this study).  |
|             | Humanitarian Use Device (HUD)   |
|             | • An FDA designation for a medical device intended to benefit patients in the treatment or diagnosis of a disease or condition that affects or is manifested in fewer than 4,000 individuals in the United States per year. For more information about Humanitarian Use Devices see the HRPP SOP manual on the R&D website. |
| Provide th  | ne following:   |
|             | a. HUD Number:  |
|             | b. HUD Sponsor or Holder:   |
|             | c. Include a copy of the FDA letter granting Humanitarian Use Device (HUD) status.  |
|             | 
 
510(k) Status –
 
A device determined by the FDA to be "substantially equivalent" to an existing device that is legally marketed in the U.S. Until a 510(k) device is approved, it is still considered investigational.
 
  |
|             | a. Provide the name of an equivalent device and sufficient documentation to justify 510(k)  |

## 76. Attach device information (i.e., brochure, device label)

Device labeling requirements are not applicable to the devices used in this study. Subjects are provided with a User Manual: Universal External Control Unit for Lower Extremity Implanted Neuroprostheses - Revision -150521, which provides user information for the external controls that power the implanted components of the FES system.

# 77. Provide a detailed description of how FDA-regulated devices will be stored, secured, dispensed, administered, tracked, and returned.

The Investigator will control the investigational device inventory. The investigator will maintain an inventory log of their clinical investigational devices. (see example log sheet attached). The log must be maintained in the project files or the project's regulatory binder for the time period required by the federal regulations or as indicated by the sponsor. The full names, titles, position, signatures, and/or initials of all VA personnel responsible for maintaining or documenting in the logs must be indicated on the cover letter or log itself.

Elements of the investigational device inventory log will include at a minimum:

- Device logs Study name
- IRB protocol #
- Sponsor name or funding agency
- Type of device
- Model number
- Serial number
- Lot number, if applicable
- Date received. (If the devices were not specifically ordered for the research protocol, but are utilized in the research protocol the date received would be the date the device is implanted in the research subject) 6.2, 6.3
- Research participant name and Medical Record Number (for internal tracking purposes)
- Research participant study I.D. number
- Date implanted or used
- Disposition. If product is returned to the sponsor or destroyed, documentation of why, when, and persons involved.
- In the event of research software, disposition may include the date the software was deprogrammed from the device (e.g. an approved pacemaker in implanted and programmed with experimental software the date disposition would be the date the subject's pacemaker is re-programmed with approved software, or in the event of an investigational software used to operate a laser the disposition should be indicated as the date removed from the machine and returned to manufacture)
- Names of all the persons who received, used, or disposed of each device.
- Date of expiration of the device

The investigational device inventory list will be updated to reflect deployment of devices to research subject, or return of devices from research subjects.

Investigational devices will be inspected for correct investigational device labeling. Labeling will state (per 21 CFR 812):

- The name and place of business of the manufacturer, packer or distributor.
- The quantity of contents
- The statement: "CAUTION--Investigational device. Limited by Federal (or United States) law to investigational use"
- The label shall describe all relevant contraindications, hazards, adverse effects, interfering substances or devices, warnings, and precautions as necessary.
- If the labeling is incorrect the devices will be quarantined until correctly labeled.
- Investigational devices will be stored in locked areas (offices, cabinets, drawers, etc.) away from general hospital supply areas.

Only study staff and assigned regulatory specialists will have access to these areas. The investigator will do an investigational device inventory, at a minimum, once yearly.

REFERENCES 21 CFR 812, Investigational Device Exemptions LSCDVAMC Policy 151-015

80. Does a normal test result indicate that the subject

